## Measures

**Oral Glucose Tolerance Test.** During each laboratory session, a 3-h 75 gm OGTT will be performed in the CRC. After an overnight fast, a blood sample for fasting glucose and insulin will be obtained at -15 mins and 0 mins immediately followed by the oral administration of 75g of

dextrose. Plasma glucose and insulin blood samples will be collected at 30, 60, 90, 120, 150 and 180 min after glucose ingestion. The primary outcome measure will be fasting glucose levels, a commonly used clinical marker. Fasting glucose levels are significantly correlated with HbA1c , which is a marker of glycemic control over 3 months that the ADA now recommends health care providers use to assess treatment effects . We will not measure HbA1c as an outcome measure in this pilot study because our 4 week intervention is unlikely to affect a measure of the 3-month average of plasma glucose levels. Secondary outcomes will be the 2-h glucose level and the Matsuda index (MI) of insulin sensitivity . These measures will allow us to ascertain whether there was an improvement in glucose metabolism. The CRC regularly performs these tests and Drs. [name] and [name] are experienced in their interpretation. As noted above, subjects who are identified as having T2DM  at the screening visit will be notified, excluded from study participation, and referred to a physician/clinic. Subjects who are identified as having prediabetes  at the screening visit will be notified, included in study participation if they meet all other inclusion criteria, and referred to a physician/clinic. [name] will oversee these referrals. Subjects who begin diabetes treatment prior to the end of the study will be dropped, however, due to common delays in seeing a physician (over one month), this is unlikely to affect many subjects. If the original HbA1c screen suggested prediabetes but the fasting and/or 2-h glucose suggest diabetes, the subject will be retained in the study, but [name] will discuss the results with the subject.

**Dim Light Melatonin Onset.** Subjects will be prompted by phone calls to refrain from NSAID use 72 h, and alcohol/caffeine 24 h, before each laboratory session and will be breathalyzed on arrival. Lights in the collection room are dimmed (<5 lux) beginning 6.5 h before and up to the subject's habitual bedtime as determined from the baseline week of actigraphy. After 30 mins in dim light, saliva samples via salivettes will be collected every 30 mins according to standard procedures . Saliva samples are frozen until delivery to Rush where they are thawed, centrifuged, refrozen and shipped in dry ice to Solidphase, Inc. (ME) who performs direct RIA assay using standard commercially available ALPCO kits . [name] will calculate the DLMOs and a trained research assistant will confirm accuracy before results are unblinded. We will calculate DLMO threshold as the mean of 3 low daytime points plus 2 times the SD of the 3 points as per consensus report . The morning light treatment will phase advance the DLMO by ~1-2 h .

**Wrist Actigraphy.** Sleep timing and duration at baseline and during the intervention will be assessed continuously using wrist actigraphy (Actiwatch Spectrum, Philips, Inc.). Due to the unobtrusive nature of this device, habitual sleep behavior can be measured over weeks. [name] has extensive experience working with actigraphy data . Actiwatch monitors feature digital integration, which is the most accurate measure of both movement level and intensity. Each subject will also complete a short sleep log every day, and call a time-stamped voice mail when they go to bed each night and when they wake up each morning .

**Food Diary.** Subjects will complete a 3-day food diary for the last 3 days of the baseline week and week 4. The food diary will ask for the amount and types of food eaten and the time of meals and snacks. Diet analysis will be performed using ESHA Food Processor version 10.7, which calculates the overall calorie intake and estimated calories obtained from each nutritional component. [name] has experience with this method and software and is using them in a current R01 project.

**Questionnaires.** Sociodemographic information will be collected only once and will include age, sex, education, employment status and the MacArthur Socioeconomic Questionnaire . Subjects will complete several questionnaires at both baseline and week 4 of the intervention, including, an assessment of physical activity (International Physical Activity Questionnaire –

Short Version), and health factors (self-rated health, Physical Health Questionnaire) in case of significant changes in health during the study. We will also include several sleep and circadian questionnaires: circadian preference based on the Horne-Ostberg Morningness-Eveningness ("owl-lark") questionnaire, Munich Chronotype Questionnaire, Pittsburgh Sleep Quality Index, and Epworth Sleepiness Scale. We will also administer Cohen's Perceived Stress Scale, and the Center for Epidemiologic Studies - Depression Scale. Finally, we will include questionnaires to assess frequency of caffeinated beverage, alcohol and tobacco consumption. The Systematic Assessment for Treatment Emergent Effects questionnaire (SAFTEE) will be administered weekly to assess potential side effects of intervention. Questionnaire responses will be entered into the password-protected REDCap database and saved according to confidential study ID number.

#### **DATA AND SPECIMEN BANKING:**

N/A No data or specimen banking will occur.

#### **DATA AND SPECIMEN MANAGEMENT:**

##### **Sample Size and Power Analysis**

We plan to enroll 34 subjects (50% female, age 35-70 y) with prediabetes. We conservatively estimate a 17% attrition rate (final n=28) which includes dropouts and noncompliance (noncompliance defined as <25% of morning light treatment, as per). This attrition rate is based on [name] light treatment trials (5% such attrition), and the work of others (4 week bright light treatment group 6% attrition, 12 week bright light treatment group 19% attrition). Note that subjects who obtain only 25% of the prescribed active light (e.g. 15 min/day) are likely to obtain some benefit, as even only 15-20 mins of morning light can be clinically effective, and only a 12 min pulse can shift the DLMO.

A primary goal of this project is to determine the effect sizes associated with morning light treatment to develop a larger RCT. However, for this pilot project we also estimated the required sample size to detect a clinically meaningful change in our primary outcome measure, fasting glucose level. We will also measure 2-h glucose and MI from the OGTT but have kept fasting glucose level as our primary outcome measure as it is a commonly used clinical measure. To estimate sample size for fasting glucose, we used a standard deviation (SD) of 9.0 mg/dl, which is the mean SD in a large sample of men and women with prediabetes. Using these values for a two-tailed independent t-test, with a total of 14 subjects per group, we will have 81% power ( $\alpha=.05$ ) to detect a change of 10 mg/dl, which is a clinically meaningful change and similar to that observed in a 2-week drug study. Thus we are well powered with an anticipated final sample size of n=28 to detect a clinically meaningful change in fasting glucose.

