## Primary Outcomes:

**Outcome 1:** We will determine the effect of active versus placebo morning light treatment on glucose metabolism in individuals with prediabetes.

[figure not shown]
**Outcome 2:** We will determine the extent to which circadian phase advances in the DLMO are related to improvements in glucose metabolism in individuals with prediabetes.

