## PROCEDURES INVOLVED:

Figure 3 presents an overview of the 5 week protocol. After screening for eligibility (see below) and informed consent, subjects will wear a wrist actigraph throughout the study. Subjects will complete a daily sleep and medication log, a questionnaire packet, and a 3-day food diary at the end of the baseline week and week 4. After the baseline week, there will be an overnight stay at the Northwestern University Clinical Research Center. Questionnaires and food diaries will be reviewed and body fat via bioimpedance will be measured. The DLMO will be assessed.

Subjects will be given dinner 4 h before bedtime and consumed 3 hours prior to bedtime to ensure duration of fasting is at least 8 h and does not exceed 14 h. In the morning, a 3 hour oral glucose tolerance test (OGTT) will be performed in the Clinical Research Unit (CRU) 2 h after wake. Subjects will then begin a 4 week morning light treatment (see details below). The first 10 subjects will be assigned active (bright), and the following 5 will be assigned placebo (dim) Re-timer®. If more subjects are enrolled in the study, the next 10 will be placed on active (bright) treatment. Subjects will receive feedback on their compliance at weekly visits. Subjects will be paid \$95 in cash at each visit to increase likelihood of participation and retention. In the final week, subjects will complete questionnaires and food diaries again. After the 4 week treatment, subjects will repeat the laboratory session for reassessment of the DLMO and OGTT.

Figure 3. Protocol Overview

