#### **Data Analysis**

**Aim 1:** For our primary analyses, we will examine the effect sizes in active treatment group. The analysis will use two-sided statistical tests and a nominal significance of 5%. Our primary analysis will focus on the pre-post measurements in the active group. As a descriptive analysis, we will estimate the mean outcome measures at each time point for each subject and test time-specific differences using non-parametric tests. If we recruit sufficient subjects for the placebo condition, we will compare the effects in the two groups.

**Aim 2:** To determine the extent to which circadian phase advances in the DLMO are related to improvements in glucose metabolism, we will first examine if the DLMO has changed significantly in the active light treatment group (and compared to placebo if possible), and then

examining if these differences are correlated with changes in glucose metabolism measures.

**Exploratory Aim:** In a similar analysis to Aim 2, we will examine possible alternative mediators (body fat, activity, total caloric intake, and sleep fragmentation [wrist actigraphy]) through which morning light treatment may impact glucose metabolism (fasting glucose, 2-h glucose, MI). We will measure body fat because it was reduced in two previous light studies (reviewed in A.2.). We will measure physical activity because light treatment has an energizing effect . We will assess total caloric intake, as differences in circadian timing can impact diet . We do not expect changes in sleep duration as subjects will be instructed to maintain their habitual sleep duration during the treatment. However, a shift in circadian timing can impact sleep consolidation  so we will assess sleep fragmentation from wrist actigraphy.

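### The 81% power claim is for a 14 v 14 comparison; the written assignment rule gives 10 v 5 or 20 v 5 (47% or 57%), and the analysis called primary is a different one

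*Combined protocol and SAP*

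**What the plan says.** Four parts of the protocol bear on this.

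- **Sample Size and Power Analysis.** Enrolment is 34, with 17% attrition leaving 28. The SD of fasting glucose is 9.0 mg/dl, taken from a large prediabetes sample, and the target is 10 mg/dl. The calculation is described as follows: "Using these values for a two-tailed independent t-test, with a total of 14 subjects per group". The stated power is 81% at alpha 0.05, and the section ends: "Thus we are well powered with an anticipated final sample size of n=28 to detect a clinically meaningful change in fasting glucose". This is the only power statement in the document.
- **Procedures Involved.** The assignment rule is sequential: "The first 10 subjects will be assigned active (bright), and the following 5 will be assigned placebo (dim"), and then "If more subjects are enrolled in the study, the next 10 will be placed on active (bright) treatment". No rule is given for later subjects.
- **Data Analysis, Aim 1.** "Our primary analysis will focus on the pre-post measurements in the active group". The two-group comparison is conditional: "If we recruit sufficient subjects for the placebo condition, we will compare the effects in the two groups". No test is named for the pre-post analysis. A separate descriptive analysis will "test time-specific differences using non-parametric tests".
- **Primary Outcomes, Outcome 1.** The first primary outcome is still the controlled comparison: "We will determine the effect of active versus placebo morning light treatment on glucose metabolism in individuals with prediabetes".

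**The concern.** A power figure describes one test at one allocation. Here the test is a two-group comparison with equal arms, while the assignment rule never places more than 5 subjects on placebo and the analysis section puts a one-group analysis first. The figure therefore supports neither the allocation as written nor the analysis called primary.

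Two readings are at risk. If active is compared with placebo, as Outcome 1 says, a null or imprecise result from 10 v 5 or 20 v 5 could be reported as coming from an adequately powered study. And the pilot is meant to supply effect sizes for a larger trial, so its users need the precision those estimates will really have. For the pre-post change that precision is not documented: the power section gives a cross-sectional SD, with neither an SD of change nor a pre-post correlation.

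**Working it through.** **Inputs.** Difference 10 mg/dl, SD 9.0 mg/dl, 14 per group, 34 enrolled and 17% attrition come from Sample Size and Power Analysis; two-sided 5% from Data Analysis; arm sizes from Procedures Involved.

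**Two-group formula.** Noncentrality = 10 / (9 × √(1/n1 + 1/n2)), df = n1 + n2 − 2. Power is the noncentral-t probability beyond the two-sided 5% critical value t. The 95% CI half-width is t × 9 × √(1/n1 + 1/n2).

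**The plan's figure.** For 14 v 14: 10 / (9 × √(2/14)) = 2.940, df 26, t = 2.056, power 80.8%. The stated 81% reproduces.

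**The written allocation.**
- 10 v 5: 10 / (9 × √(1/10 + 1/5)) = 2.029, df 13, t = 2.160.
- 20 v 5: 10 / (9 × √(1/20 + 1/5)) = 2.222, df 23, t = 2.069.

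| Active v placebo | Power for 10 mg/dl | 95% CI half-width (mg/dl) | Difference detectable at 80% power (mg/dl) |
|---|---|---|---|
| 14 v 14 | 80.8% | 7.0 | 9.9 |
| 10 v 5 | 46.8% | 10.6 | 14.9 |
| 20 v 5 | 56.7% | 9.3 | 13.2 |

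With 5 placebo subjects and unlimited active subjects, power tends to P(Z > 1.96 − 10/(9 × √(1/5))) = 70%. Adding active subjects alone cannot restore 81%.

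**Attrition.** The 81% is after attrition; the 47% and 57% are before it, which favours the plan. Since 0.83 × 10 = 8.3, 0.83 × 5 = 4.2 and 0.83 × 20 = 16.6, the like-for-like arms are about 8 v 4 (37.5%) and 17 v 4 (47.5%). The analysed numbers may be higher: Subjects and Screening and Potential Benefits carry the last observation forward for some dropped subjects, and Withdrawal of Participants leaves the use of withdrawn subjects' data open.

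**Subjects 26 to 34.** Nine planned subjects have no rule. Starting from 20 v 5:

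| Nine unassigned subjects | Before attrition | After about 17% loss |
|---|---|---|
| All active | 29 v 5: 60.5% | 24 v 4: 51% |
| Four placebo | 25 v 9: 79% | 21 v 7: 69% |
| Five placebo | 24 v 10: 82% | 20 v 8: 72% |
| All placebo | 20 v 14: 87% | 17 v 11: 79%; 16 v 12: 80% |

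**Other two-group analyses.** These need a pre-post correlation, which the documents do not give; 0.3 to 0.7 is assumed. Comparing changes (SD 9 × √(2(1 − ρ))) gives 36–68% at 10 v 5 and 44–78% at 20 v 5. Baseline adjustment (residual SD 9 × √(1 − ρ²), one df fewer) gives 50–74% and 61–84%.

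**Pre-post in the active arm.** Assume a paired t-test, SD 9.0 at both visits and ρ from 0 to 0.7. The SD of change is then 9 × √(2(1 − ρ)), that is 12.7 down to 7.0 mg/dl. The noncentrality is 10√n / SD of change, df = n − 1.

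| Active subjects | Power, ρ = 0 to 0.7 | 95% CI half-width (mg/dl) |
|---|---|---|
| 8 | 48% to 93% | 10.6 to 5.8 |
| 10 | 60% to 98% | 9.1 to 5.0 |
| 17 | 86% to >99% | 6.5 to 3.6 |
| 20 | 91% to >99% | 6.0 to 3.3 |

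An exact signed-rank test, simulated with 4,000 trials and normal changes, gives 59–97% with 10 subjects and at least 90% with 20.

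**The case against.** The best defence is that this is a pilot whose declared goal is to estimate effect sizes, that the placebo comparison is explicitly conditional, and that the pre-post analysis called primary may have ample power. On that view the 81% is a leftover sentence that changes no analysis and harms no participant.

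Part of this stands. The pilot purpose and the conditional wording limit the damage, and nothing here shows the pre-post analysis to be underpowered. But the plan chose to make a formal power claim despite being a pilot, and attached it to a comparison that one section lists as a primary outcome and another makes optional. The condition is also undefined: nothing says how many placebo subjects would be enough.

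A second defence is that 10 v 5 and 20 v 5 apply only if enrolment stops at 15 or 25, whereas 34 are planned. That is fair: at 34 the allocation is unspecified rather than shown to be 20 v 5. It does not rescue the figure. On the plan's own post-attrition basis, only sending all nine remaining subjects to placebo brings power close to 81% (about 79–80%), and no text provides for that. Splitting them about evenly gives roughly 70%.

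Baseline adjustment could also recover power, but the plan specifies no such analysis, and it passes 81% only near the top of the assumed correlation range with 20 active subjects.

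**Conclusion.** The concern holds. The 81% is computed correctly for a design that the protocol does not describe. For the same test and inputs, the written rule yields 47% if enrolment stops at 15 and 57% if it stops at 25, before attrition. The interval half-width rises from 7.0 to 10.6 or 9.3 mg/dl; at 10 v 5 it exceeds the 10 mg/dl that the plan regards as clinically meaningful. These results use only the plan's inputs and a t-test with common SD.

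The power of the analysis called primary is undocumented. It depends on the number of active subjects and on a pre-post correlation found nowhere in the documents, so the pre-post ranges above are illustrations under stated assumptions. Because the sole sample-size justification fits neither the allocation nor the primary analysis, it must be corrected.

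**What to change.** In Sample Size and Power Analysis, remove the 81% and the conclusion that follows from it, or label both as applying only to a 14 v 14 design that the assignment rule does not follow. Then state:

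1. For the active-arm pre-post analysis: the test, and its power or 95% CI half-width at the planned number of active subjects, over a stated range of pre-post correlation or with a sourced SD of change.
2. For active versus placebo: the same at the actual allocation, saying whether final values, changes or baseline-adjusted values are compared, and describing the comparison as low-precision.
3. Whether dropped subjects count in these numbers through last observation carried forward.

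Make Primary Outcomes and Data Analysis agree on whether the placebo comparison is primary or conditional; if conditional, say how many placebo subjects suffice. Reconcile the planned 34 with an assignment rule that ends at subject 25.

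Items 1 to 3 are changes of wording and need no extra subjects; their cost is a less favourable two-group power statement. The assignment of subjects 26 to 34 and the status of the placebo comparison are design decisions for the sponsor.

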#### **Data Analysis**

**Aim 1:** For our primary analyses, we will examine the effect sizes in active treatment group. The analysis will use two-sided statistical tests and a nominal significance of 5%. Our primary analysis will focus on the pre-post measurements in the active group. As a descriptive analysis, we will estimate the mean outcome measures at each time point for each subject and test time-specific differences using non-parametric tests. If we recruit sufficient subjects for the placebo condition, we will compare the effects in the two groups.

**Aim 2:** To determine the extent to which circadian phase advances in the DLMO are related to improvements in glucose metabolism, we will first examine if the DLMO has changed significantly in the active light treatment group (and compared to placebo if possible), and then

examining if these differences are correlated with changes in glucose metabolism measures.

**Exploratory Aim:** In a similar analysis to Aim 2, we will examine possible alternative mediators (body fat, activity, total caloric intake, and sleep fragmentation [wrist actigraphy]) through which morning light treatment may impact glucose metabolism (fasting glucose, 2-h glucose, MI). We will measure body fat because it was reduced in two previous light studies (reviewed in A.2.). We will measure physical activity because light treatment has an energizing effect . We will assess total caloric intake, as differences in circadian timing can impact diet . We do not expect changes in sleep duration as subjects will be instructed to maintain their habitual sleep duration during the treatment. However, a shift in circadian timing can impact sleep consolidation  so we will assess sleep fragmentation from wrist actigraphy.

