**Light Treatment.** The 1 h daily morning light treatment will start within a few minutes after each subject's average wake time, as determined from the baseline week of actigraphy. The light treatment may start up to 1 h earlier to accommodate the subject's usual morning schedule (work, child care) if required. Subjects are provided with an alarm set to the start of the morning treatment. A light log to note light on/off times and any interruptions to the light treatment will be provided. Subjects will be instructed to maintain their baseline sleep duration throughout the light treatment. Daily bed and wake time phone calls to a time-stamped voice mail will be reviewed daily with phone calls to subjects if required to ensure compliance. Wrist actigraphy data will be reviewed weekly in the presence of the subject. Importantly, the Re-timer® light device is commercially available. The adjustable nose pad on each Re-timer® (whether active or placebo) will be individually fit to each subject to optimize the light treatment (Appendix). After the introduction to the Re-timer® (whether active or placebo), subjects will complete a treatment expectation item of 0 "expect no change" to 10 "expect to be healthier". In between weekly visits, subjects will be encouraged to call research staff 24/7 with any questions about the light treatment. At the start of the second laboratory session, subjects will complete a treatment satisfaction item of 0 "not at all satisfied" to 10 "extremely satisfied".

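### The plan defines and powers an active-versus-placebo comparison, but its primary analysis is the uncontrolled pre-post change in the active arm, and the placebo comparison is optional

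*Combined protocol and SAP*

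**What the plan says.** Four parts of the combined protocol and SAP, all current text, bear on this.

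- **Study Endpoints, Primary Outcomes (Outcome 1):** "We will determine the effect of active versus placebo morning light treatment on glucose metabolism in individuals with prediabetes".
- **Sample Size and Power Analysis:** the calculation is for a "two-tailed independent t-test, with a total of 14 subjects per group, we will have 81% power" to detect 10 mg/dl in fasting glucose with SD 9.0. The section concludes that 28 evaluable subjects make the study well powered. It also gives a purpose: "A primary goal of this project is to determine the effect sizes associated with morning light treatment to develop a larger RCT".
- **Procedures Involved:** "The first 10 subjects will be assigned active (bright), and the following 5 will be assigned placebo (dim") and then "If more subjects are enrolled in the study, the next 10 will be placed on active (bright) treatment". This accounts for 10 + 5 + 10 = 25 of the 34 planned subjects; the other 9 have no stated arm.
- **Data Analysis, Aim 1:** "Our primary analysis will focus on the pre-post measurements in the active group". The two groups are compared only if placebo recruitment turns out to be sufficient. No threshold is given, and this section states no model for the comparison.

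**The concern.** The objective, the power basis, the assignment rule and the primary analysis do not describe the same study. The objective and the power statement need two groups of 14. The assignment rule supplies 5 placebo subjects. The primary analysis uses none of them.

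The active-arm change mixes the light effect with everything else that starts or continues after the baseline glucose tolerance test. Procedures Involved adds "Subjects will receive feedback on their compliance at weekly visits". The Light Treatment text adds an alarm, daily review of bed and wake calls to secure compliance, and "Subjects will be instructed to maintain their baseline sleep duration throughout the light treatment". Treatment expectation is recorded on a 0 to 10 item, so the protocol itself treats it as relevant. Effects of the prediabetes notice, referral and monitoring that began before the baseline test may also continue, and there may be time trends. The protocol made a dimmed device so that expectations would be similar in the two groups, yet the primary analysis does not use that control.

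Two things are at stake. Outcome 1 may go unanswered, and because the threshold for comparing groups is undefined, the choice could be made after results are seen. Also, the effect size passed to the larger RCT would be an active-arm change, while that trial would estimate a between-arm difference.

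**Working it through.** **Inputs from the documents.** SD 9.0 mg/dl, difference 10 mg/dl, two-sided 5%, 14 per group, 34 enrolled, 17% attrition (Sample Size and Power Analysis); 10 active, 5 placebo, then 10 active (Procedures Involved).

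**1. The plan's own figure.** SE = 9 × √(1/14 + 1/14) = 3.40. Noncentrality = 10/3.40 = 2.94 on 26 df. Noncentral-t power = 80.8%, so the stated 81% reproduces. It is correct for 14:14.

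**2. The same test at the arm sizes the assignment rule gives.** SE = 9 × √(1/n₁ + 1/n₂).

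| Active : placebo | SE | Noncentrality | df | Power for 10 mg/dl | Detectable at 80% power (mg/dl) |
|---|---|---|---|---|---|
| 14 : 14 | 3.40 | 2.94 | 26 | 81% | 9.9 |
| 10 : 5 | 4.93 | 2.03 | 13 | 47% | 14.9 |
| 20 : 5 | 4.50 | 2.22 | 23 | 57% | 13.2 |
| 8 : 4 (10:5 after 17% attrition) | 5.51 | 1.81 | 10 | 37% | 17.1 |
| 17 : 4 (20:5 after 17% attrition) | 5.00 | 2.00 | 19 | 48% | 14.8 |

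If all 9 unassigned subjects went to active (29:5, an assumption), power would be 60%.

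**3. The declared primary analysis.** The documents give it no power or precision, and no SD of change. Assume a pre-post correlation ρ from 0 to 0.7, so SD of change = 9 × √(2(1 − ρ)), which runs from 12.7 down to 7.0. Paired-t power for a 10 mg/dl change is then 60% to 98% with 10 active subjects, and 91% to more than 99% with 20. The weakness of this analysis is not power but what the change represents.

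**4. Illustration of a shift shared by both arms.** The documents give no such shift, so its size is assumed.

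- No light effect and a shared fall of 3 mg/dl: the paired test is significant in 10% to 23% of trials with 10 active subjects and 17% to 45% with 20, against a nominal 5%.
- A shared fall of only 1 mg/dl: 6% to 7% with 10, and 6% to 9% with 20.
- A true benefit of 5 mg/dl and a shared rise of 3 (net fall of 2), 10 active subjects: power drops from 20–53% to 7–13%.

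**5. Consequence for the larger RCT (same kind of illustration).** If 3 of an observed 10 mg/dl were shared, the between-arm effect would be 7. A trial sized on 10 needs 14 per group. With a true difference of 7, that trial has 51% power, and 27 per group are needed for 80%.

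**6. Precision of the between-arm estimate.** The unadjusted 95% half-width is t × SE: 2.160 × 4.93 = 10.6 mg/dl at 10:5, and 2.069 × 4.50 = 9.3 at 20:5. Adjusting for baseline replaces 9 by 9 × √(1 − ρ²) and costs one df. At ρ = 0.5 and 0.7 this gives 9.3 and 7.7 (10:5), or 8.1 and 6.7 (20:5).

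**The case against.** The strongest reply is that this is a declared pilot whose aim is to estimate effect sizes. The assignment rule and the Data Analysis section agree with each other: a small placebo group and an active-arm analysis. On this view, Outcome 1 and the power statement are the outliers. Rewording them as an active-arm pilot estimate would remove the contradiction, whereas promoting a small, sequentially assigned contrast gives prominence to a weak estimate. Rewording would make the text consistent. It would still leave light inseparable from the accompanying procedures and from time, and would not supply the between-arm effect the larger RCT needs.

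Three narrower objections:

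- **Adjusted power is higher.** This is true: for a baseline-adjusted analysis at ρ = 0.5 to 0.7 it is 58% to 74% at 10:5 and 69% to 84% at 20:5. But the plan's 81% is for an unadjusted t-test, so unadjusted power is the right comparator for that claim.
- **The 3 mg/dl shift is assumed.** It is, and a 1 mg/dl shift does little. The finding does not depend on it.
- **Reporting with very few placebo completers is unhelpful.** With one completer, the adjusted half-width would be about 16 to 19 mg/dl (10 active) or 14 to 17 (20 active). The interval would show that weakness plainly.

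It also stands that the power section does name a test for two groups; the missing model is in the Data Analysis section.

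**Conclusion.** The concern holds and should be fixed before analysis. The 81% is computed correctly, but for a 14:14 comparison that the stated assignment does not provide and the primary analysis does not use. At the stated arm sizes the same test has 47% power (10:5) or 57% (20:5), and 37% or 48% after the planned attrition. These figures use only the plan's SD, difference and significance level, plus rounding of the attrition.

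Independently of power, the plan can be followed exactly and leave Outcome 1 unestimated. The inflated false-positive rates and the under-sized RCT are illustrations under an assumed shared shift and a range of correlations. They show how an uncontrolled change could mislead, not how large the error will be.

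**What to change.** - **Aim 1:** make the Outcome 1 estimate the active-minus-placebo difference in week-4 fasting glucose, adjusted for baseline fasting glucose (ANCOVA), with a 95% confidence interval. Use the same model for 2-h glucose and the Matsuda index.
- **Condition:** delete the requirement of sufficient placebo recruitment. Report the contrast whenever any placebo subjects complete; if none do, state that Outcome 1 was not estimated.
- **Pre-post change:** keep it as secondary, labelled uncontrolled and not an effect of light.
- **Interpretation:** state that assignment by enrolment order makes the contrast non-randomised and open to calendar-time confounding, which baseline adjustment does not remove, so its interval and p-value are descriptive.
- **Numbers:** reconcile Primary Outcomes, Procedures Involved, Sample Size and Data Analysis on the number per arm, including the 9 unassigned subjects, and restate the power for the numbers actually planned.

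The cost is SAP wording, a corrected power statement and one regression per outcome on data already collected. ANCOVA is preferred to change scores for efficiency only: relative variance is 1 − ρ² against 2(1 − ρ), that is 0.75 against 1.0 at ρ = 0.5, and 0.51 against 0.60 at ρ = 0.7. The price is a wide interval, openly shown. Since this version is dated May 3, 2018 and recruitment was to finish by 05/31/2018, record the change and its date as a late one.
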